**Analysis Method:**

For each subject with paired data, the change from baseline (improved, no change, worsened) will be evaluated at 12 months. This primary endpoint of improvement in MR (grade) will be presented with frequencies and percentages of subjects with improved MR at 12 months. Two-sided 95% exact binomial confidence intervals of the percent of subjects overall and in each of the three subgroups with improved MR at 12 months will also be reported.

**### 7.9.2 Primary Endpoint #2**

All-cause mortality rate at 12 months post procedure.

**Hypothesis/Decision criteria:**

No specific hypotheses or pass/fail criteria have been set. The analysis will be descriptive and no statistical hypothesis test will be performed.

**Endpoint Definition/Parameters to Be Estimated:**

All-cause mortality event rate estimate will be provided at 12 months post procedure.

**Data Collection and Analysis Dataset:**

Data will be collected on an AE CRF.

This objective will be analyzed for the Successfully Implanted (IMP) cohort, and for the IMP subjects with CG Future Band, CG Future Ring and Profile 3D Ring respectively.

**Analysis Method:**

A Kaplan-Meier analysis will be performed.

**### 7.9.3 Secondary Endpoint #1**

Characterization of subject demographics and pathophysiology of mitral valve disease.

**Hypothesis/Decision criteria:**

No specific hypotheses or pass/fail criteria have been set. The analysis will be descriptive and no statistical hypothesis test will be performed.

**Endpoint Definition/Parameters to Be Estimated:**

Baseline demographics and clinical variables will be summarized. The following subject characteristics at baseline will be reported: age (in years), gender, previous cardiovascular surgery, symptoms of heart failure, cardiac rhythm, New York Heart Association (NYHA) classification, risk factors, level of regurgitation, type of mitral valve deficiency, etc.

**Data Collection and Analysis Dataset:**

Data will be collected on a DEMOGRAPHICS (DM) or PRE-OPERATIVE CLINICAL HISTORY (MH) CRF. This objective will be analyzed for the Successfully Implanted (IMP) cohort.

**Analysis Method:**

Descriptive statistics will be provided. For continuous variables (e.g. age), the mean, median, standard deviation, minimum, maximum, and first and third quartiles will be presented. For categorical variables, the number and percentage of subjects in the category of interest will be presented, as described in section 7.2.

**7.9.4 Secondary Endpoint #2**

Improvement in mitral valve regurgitation (MR) (grade) at discharge and first follow up (3-6 months).

**Hypothesis/Decision criteria:**

No specific hypotheses or pass/fail criteria have been set. The analysis will be descriptive and no statistical hypothesis test will be performed.

**Endpoint Definition/Parameters to Be Estimated:**

Mitral valve function will be based on site echocardiographic recordings. The parameter to be estimated is the grade of mitral valve regurgitation using echo, in subjects at discharge and 3-6 months post procedure. The grades of MR, 0-4, will correspond to the ASE guidelines (as described in Table 1 in CIP) ranging from no MR, Mild MR, Moderate MR, Moderate-to-Severe MR and Severe MR.

**Data Collection and Analysis Dataset:**

Data will be collected on an ECHOCARDIOGRAM (CV) CRF.

This objective will be analyzed for the Successfully Implanted (IMP) cohort, and for the IMP subjects with CG Future Band, CG Future Ring and Profile 3D Ring respectively. IMP subjects having available MR collection at baseline, discharge and 3-6 months post procedure will be included in the analysis.

**Analysis Method:**

For each subject with paired data, the change from baseline (improved, no change, worsened) will be evaluated at discharge and 3-6 months follow up. This secondary endpoint of improvement in MR (grade) will be presented with frequencies and percentages of subjects with improved MR at discharge and 3-6 months. Two-sided 95% exact binomial confidence intervals of the percent of subjects overall and in each of the three subgroups with improved MR at discharge and 3-6 months will also be reported.

## 7.9.5 Secondary Endpoint #3

Improvement in New York Heart Association (NYHA) functional class at discharge, first follow up (3-6 months) and second follow up (12 months) compared to baseline.

### Hypothesis/Decision criteria:

No specific hypotheses or pass/fail criteria have been set. The analysis will be descriptive and no statistical hypothesis test will be performed.

### Endpoint Definition/Parameters to Be Estimated:

The parameter to be estimated is NYHA classification at discharge, 3-6 months and 12 months follow-up.

New York Heart Association (NYHA) classification and risk factors are defined as below:

Classification	Description
Class I	Patients with cardiac disease, but without resulting limitations of physical activity. Ordinary physical activity does not cause undue fatigue, palpitation, dyspnea, or anginal pain.
Class II	Patients with cardiac disease resulting in slight limitation of physical activity. Patients are comfortable at rest. Ordinary physical activity results in fatigue, palpitation, dyspnea, or anginal pain.
Class III	Patients with cardiac disease resulting in marked limitation of physical activity. Patients are comfortable at rest. Less than ordinary physical activity causes fatigue, palpitation, dyspnea, or anginal pain.
Class IV	Patients with cardiac disease resulting in inability to perform any physical activity without discomfort. Symptoms of cardiac insufficiency or of the angina syndrome may be present even at rest. If any physical activity is undertaken, discomfort is increased.

### Data Collection and Analysis Dataset:

Data will be collected on a DEMOGRAPHICS (DM) or DISCHARGE/FOLLOW UP (SV) CRF.

This objective will be analyzed for the Successfully Implanted (IMP) cohort. All IMP subjects with available NYHA collections (I/II/III/IV) or died at baseline, discharge, 3-6 months and 12 months follow up visits will be included in the analysis.

### Analysis Method:

For each subject with paired data or who died prior to a visit, the change from baseline (improved, no change, worsened or died) will be calculated at discharge, 3-6 months, and 12 months. The endpoint of improvement in NYHA class will be presented with frequencies and percentages of subjects with improved NYHA at discharge, 3-6 months, and 12 months. The two-sided 95% exact binomial confidence interval of the overall percent of subjects with improved NYHA class at discharge, 3-6 months, and 12 months will also be reported.

**7.9.6 Secondary Endpoint #4**

Hospitalization for Heart Failure at 6 and 12 months post procedure.

Hypothesis/Decision criteria:

No specific hypotheses or pass/fail criteria have been set. The analysis will be descriptive and no statistical hypothesis test will be performed.

Endpoint Definition/Parameters to Be Estimated:

Hospitalization for Heart Failure event rate estimate will be provided at 6 and 12 months post procedure.

Data Collection and Analysis Dataset:

Data will be collected on an AE CRF.

This objective will be analyzed for the Successfully Implanted (IMP) cohort.

Analysis Method:

A Kaplan-Meier analysis will be performed.

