**Table 3: NYHA functional class definitions**

Classification	Description
Class I	Patients with cardiac disease, but without resulting limitations of physical activity. Ordinary physical activity does not cause undue fatigue, palpitation, dyspnea, or anginal pain.
Class II	Patients with cardiac disease resulting in slight limitation of physical activity. Patients are comfortable at rest. Ordinary physical activity results in fatigue, palpitation, dyspnea, or anginal pain.
Class III	Patients with cardiac disease resulting in marked limitation of physical activity. Patients are comfortable at rest. Less than ordinary physical activity causes fatigue, palpitation, dyspnea, or anginal pain.
Class IV	Patients with cardiac disease resulting in inability to perform any physical activity without discomfort. Symptoms of cardiac insufficiency or of the angina syndrome may be present even at rest. If any physical activity is undertaken, discomfort is increased.

- Hospitalization for Heart Failure at 6 months and at 12 months post procedure

Hospitalizations for Heart Failure are defined as a non-elective hospital admission for signs and symptoms related to heart failure that results in a one-night stay (i.e., where the admission date and the discharge date differ by at least one calendar day). For the purpose of the protocol, overnight stays at nursing home facilities or extended care facilities do not meet the protocol definition of hospitalization. The occurrence of hospitalization for heart failure will be evaluated at 6 months and 12 months post procedure.

- Mitral valve re-intervention at discharge, 6 months and at 12 months post procedure

Following the completion of the procedure, defined as the subject leaving the operating theater with an implanted Profile 3D™ or CG Future® annuloplasty system, any surgical or percutaneous interventional catheter procedure that repairs, otherwise alters or adjusts, or replaces the previously implanted annuloplasty system will be termed re-intervention. In addition to surgical

reoperations, enzymatic, balloon dilatation, interventional manipulation, repositioning, or retrieval, and other catheter-based interventions for valve-related complications are also considered re-interventions. The re-intervention rate will be evaluated at discharge, 6 months and 12 months post procedure.

- Stroke at 6 months and at 12 months post procedure

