## 9.11. Subject Withdrawal or Discontinuation

All subjects will be encouraged to remain in the registry through the last follow-up visit at 12 months. Subjects who discontinue participation prematurely after attempted implant will be included in the analysis of results (as appropriate) but they will not be replaced in the enrollment of total study subjects. If a study subject is discontinued from the study early, the reason for discontinuation should be documented in the subject file and a Study Exit eCRF must be completed. If discontinuation is because of safety concerns, the subject shall be asked to be followed for collection of ongoing safety data outside the study. Any data collected after the exit date will not be analyzed as part of the study.

In case the subject undergoes device explant, the subject will be exited from the study.

The subjects will be exited from the study following their 12 month follow up visit. This 12 month visit will be primarily conducted via in-office visit and has a window period of additional 1 month, up to day 395 post implant. All adverse event information will be collected and reported during this follow up visit, as per timelines described above in section 11.2; subjects will be considered exited from the study on completion of their 12 month visit or when they are considered lost to follow up (after three failed attempts are made to contact the subjects).

The investigating site and Sponsor will make every effort to have all subjects complete the follow up visit schedule. A subject will not be considered lost-to-follow-up unless all efforts to obtain compliance are unsuccessful. At a minimum, the effort to obtain follow-up information must include three attempts to make contact via telephone and if contact via phone is not successful, a traceable letter from the Investigator must be sent to the subject's last known address. Should both telephone and mail efforts to contact the subject be unsuccessful, the subject's primary physician should be contacted. Subjects will then be deemed lost to follow up. All contact efforts to obtain follow-up must be documented in the subject's medical records.

If a subject discontinues the study at any time, is withdrawn from the study early, or completes all protocol required follow-up they should then be followed per the local standard of care for their condition.

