### 7.2 General Methodology

Descriptive statistics will be used to report study data. For continuous variables (e.g. age), the mean, median, standard deviation, minimum, maximum, and first and third quartiles will be presented. For categorical variables, the number and percentage of subjects in the category of interest will be presented. For time to event data, Kaplan-Meier analyses of event or event-free rates at discharge, 6 and 12 months will be presented. For these analyses, the time points will correspond to 7 days, 183 days and 365 days post implantation respectively. At each time point with data, the product limit estimate of the event or event-free rates, and the loglog transformed 95% confidence interval using the Peto standard error will be presented. For subjects without an event, the date of censoring will be the latest date of all follow-up visits (including phone and/or mail correspondence), assessments, events (including death) and study exits. For subjects whose exit reason is lost to follow-up, the last follow-up date will be the latest date of the follow-up visits (including phone and/or mail correspondence), assessments and events.

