**7.9.7 Secondary Endpoint #5**

Mitral valve re-intervention at discharge, 6 and 12 months post procedure.

Hypothesis/Decision criteria:

No specific hypotheses or pass/fail criteria have been set. The analysis will be descriptive and no statistical hypothesis test will be performed.

Endpoint Definition/Parameters to Be Estimated:

Mitral valve re-intervention event rate estimate will be provided at discharge, 6 and 12 months post procedure.

Data Collection and Analysis Dataset:

Data will be collected on a RE-INTERVENTION (RE-OP) CRF.

This objective will be analyzed for the Successfully Implanted (IMP) cohort.

Analysis Method:

A Kaplan-Meier analysis will be performed.

The number and percentage of subjects with mitral valve re-intervention post implant on or prior to discharge will also be presented, as described in section 7.2.

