## **7.12 Changes to Planned Analysis**

Analysis set defined in the CIP for the primary and secondary endpoints is changed to the Successfully Implanted set in order to align with other surgical valve studies.

New onset of atrial fibrillation will be evaluated using Kaplan-Meier method instead of percent of subjects as described in the CIP in order to incorporate subject censoring in the course of the study. Atrial fibrillation identified on the post-procedural ECG or AE forms will be included in the analysis.

Changes to V1.0 of the SAP include: Baseline data will be presented for the Enrolled and Successfully Implanted cohorts, and procedural data will be presented for the Attempted Implant and Successfully Implanted cohorts. As one of the objectives of the registry is to characterize subjects who are considered eligible for mitral valve repair in South Asia, analyzing baseline and procedural characteristics on these analysis cohorts will cover the populations of interest.

Sub-group analyses will be performed on the Successfully Implanted subjects with CG Future Band, CG Future Ring and Profile 3D Ring respectively for the primary and selected secondary endpoints.

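### Kaplan-Meier for HF hospitalization, re-intervention, stroke and new-onset AF censors deaths, so the reported rates slightly overstate the proportion of patients who have the event

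*Combined protocol and SAP*

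**What the plan says.** SAP 7.9.6 (HF hospitalization), 7.9.7 (re-intervention), 7.9.8 (stroke) and 7.9.9 (new-onset AF) each give the same analysis method: "A Kaplan-Meier analysis will be performed". For re-intervention there is one addition, a crude count limited to the hospital stay: "The number and percentage of subjects with mitral valve re-intervention post implant on or prior to discharge will also be presented". For AF, SAP 7.12 records a change of method: "New onset of atrial fibrillation will be evaluated using Kaplan-Meier method instead of percent of subjects as described in the CIP"; the reason given is to take account of censoring.

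SAP 7.2 sets one censoring rule for all time-to-event endpoints. It begins "For subjects without an event, the date of censoring will be the latest date of all follow-up visits", and its list of dates ends with "assessments, events (including death) and study exits". A subject who dies without the event is therefore censored at death. The estimates are read at days 7, 183 and 365. Neither document names a competing-risk estimator, and for HF hospitalization, re-intervention and stroke the SAP defines the target only as an event rate estimate.

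On explant, CIP 9.11 says "In case the subject undergoes device explant, the subject will be exited from the study" and "Any data collected after the exit date will not be analyzed as part of the study". CIP 5.2.2 defines re-intervention broadly: any surgical or catheter procedure "that repairs, otherwise alters or adjusts, or replaces the previously implanted annuloplasty system will be termed re-intervention", with retrieval also listed.

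**The concern.** A patient who has died cannot later have a stroke or an HF admission. Censoring at death treats that patient as still able to have the event, with the same future risk as those who remain. One minus Kaplan-Meier then describes a population in which nobody dies, under an independence assumption that the SAP does not state.

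The registry is meant to give real-world data on clinical outcomes, and a reader will take a 12-month rate as the share of implanted patients who had the event. Cumulative incidence is the quantity that matches that reading. The SAP already recognises the issue elsewhere: for NYHA class (SAP 7.9.5) death is kept as an outcome category. What is at stake is a small error, always in the same direction as far as deaths are concerned, that the confidence interval does not reflect.

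**Working it through.** **No design figure to reproduce.** The sample size of 200 was not statistically derived (CIP 13.4, SAP 6), and no expected rate is given for any of the four endpoints or for mortality. The event rates below are assumptions.

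**Mortality input (assumption).** CIP 4.1 cites a cohort of 121 annuloplasty patients with cardiomyopathy: 3.3% mortality at 30 days, and survival of 95% at 3 months and 91% at 30 months. I use a constant hazard within each interval, with 3 months as day 91 and 30 months as day 913:

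- Days 0–30: −ln(0.967)/30 = 0.0011186 per day
- Days 30–91: −ln(0.95/0.967)/61 = 0.0002908 per day
- Days 91–913: −ln(0.91/0.95)/822 = 0.0000523 per day

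The cumulative hazard at day 365 is 30 × 0.0011186 + 61 × 0.0002908 + 274 × 0.0000523 = 0.0656. Mortality is 1 − exp(−0.0656) = 6.4%.

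**Formulas.** With event hazard h and death hazard d(t):

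- One minus Kaplan-Meier = 1 − exp(−365h)
- Cumulative incidence = ∫ h · exp(−ht − D(t)) dt from 0 to 365, where D(t) is the cumulative death hazard

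The second integrand is the first multiplied by exp(−D(t)) ≤ 1, so the direction is fixed.

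**Worked case, Kaplan-Meier rate 10%.** h = −ln(0.90)/365 = 0.00028866. Within an interval of length L, the contribution is S · h/(h+d) · (1 − exp(−(h+d)L)), where S is the probability of being alive and event-free at its start. The three intervals give 0.85%, 1.66% and 6.99%, which sum to 9.49%. The excess is 0.51 points.

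| Kaplan-Meier rate | Cumulative incidence | Excess (points) | Relative excess |
|---|---|---|---|
| 5% | 4.75% | 0.25 | 5% |
| 10% | 9.49% | 0.51 | 5% |
| 20% | 19.00% | 1.00 | 5% |

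**Sensitivity.**

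- Events early (80% within 30 days): excess about 0.1 point at a 5% rate and 0.2 at 10%, roughly 2% relative.
- A 20% rate arising entirely by day 7: h = −ln(0.80)/7 = 0.03188; cumulative incidence = 0.03188/(0.03188 + 0.00112) × (1 − exp(−7 × 0.03300)) = 19.92%; excess 0.08 points.
- Death hazard doubled or tripled (12.3% or 17.9% mortality at day 365): a 10% Kaplan-Meier rate is 0.98 or 1.44 points too high.

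**Simulation check.** In 2,000 simulated registries of 200 subjects at each of the rates 5%, 10% and 20%, with about 5% lost to follow-up, one minus Kaplan-Meier was never below the Aalen-Johansen estimate. The mean differences were 0.26, 0.51 and 1.00 points.

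**Against sampling error.** The half-width 1.96 × √(p(1 − p)/200) is 3.0 points at 5%, 4.2 at 10% and 5.5 at 20%. This is a simple approximation to the planned log-log interval, and the implanted set may be smaller than 200.

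**Explant, taken separately.** For HF hospitalization, stroke and AF an explanted patient is alive and still at risk. Assume a 10% Kaplan-Meier rate, 5% explanted by day 365, and no deaths. Kaplan-Meier minus the true share with the event, before or after explant, is:

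- +0.25 points if risk stops at explant
- 0 if risk is unchanged
- −0.45 if the hazard triples after explant
- −0.84 if it rises fivefold

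The direction is not fixed.

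**The case against.** The strongest reply is that Kaplan-Meier is a legitimate descriptive estimate of event risk with death censored. SAP 7.2 promises a product-limit estimate and nowhere promises the proportion of patients with the event. The study has no hypothesis test or pass/fail criterion, so no decision turns on half a point. Related information is already planned: all-cause mortality as a primary endpoint, disposition counts of deaths and explants (SAP 7.1.1), and proportions with adverse events by MedDRA term (SAP 7.10). All of this stands, and it is why the point is minor. It does not remove the mismatch, because the SAP does not tell the reader that its rates assume death away, and those summaries do not give an endpoint-specific cumulative incidence at days 183 and 365.

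A reader might infer that exit at explant inflates the rates in the same way as death. The documents do not support that. Under CIP 5.2.2 an explant will normally be the re-intervention event itself, so it is counted and not censored. For the other three endpoints it is possibly informative loss to follow-up, which can bias the rate either way.

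A second caution concerns AF. SAP 7.9.9 analyses the whole implanted cohort and does not say that subjects with prior AF leave the risk set. If they stay, the rate is pulled down, and the net direction for AF as reported is unknown. The effect of censoring deaths is still upward.

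**Conclusion.** The point holds for deaths, and as a minor improvement. For all four endpoints, censoring death makes one minus Kaplan-Meier at or above the cumulative incidence. The direction follows from algebra; the size rests on assumptions. At the borrowed mortality of about 6.4% and a constant event hazard, the excess is 0.25 to 1.0 point for rates of 5% to 20%, about 5% relative, and about 2% or less if events come early. It would be larger if mortality here were higher. In the cases at the borrowed mortality it is well inside sampling error.

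A reader might go further and call Kaplan-Meier invalid here, or quote a relative error above 10%. Neither is supported. Kaplan-Meier answers a different question that the SAP leaves unlabelled. An 11% excess requires 10% mortality with every death before every event (for example 20% against 0.90 × 20% = 18%), which is an extreme bound and not an expectation.

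**What to change.** In SAP 7.9.6 to 7.9.9:

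1. Report the Aalen-Johansen cumulative incidence with death alone as the competing event, with 95% confidence intervals at the planned days (7, 183 and 365, as each endpoint requires). This also meets the reason given in SAP 7.12 for moving AF to Kaplan-Meier, since the estimator handles censoring.
2. Keep Kaplan-Meier as a supplement, labelled as censoring death, for comparison with other surgical valve series.
3. Do not make explant a competing event. Count it as re-intervention where it meets the CIP 5.2.2 definition, including when its date is also the exit date. For HF hospitalization, stroke and AF, state that exit at explant is treated as censoring and may be informative.
4. Leave all-cause mortality as Kaplan-Meier.

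The cost is SAP wording and a standard procedure. Dates of events, death and exit are already collected, and no visits or subjects are added. The downside is a second set of estimates, and lead figures slightly less directly comparable with older Kaplan-Meier series.
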